### C. Human Subjects

1. Only subjects who satisfy stringent inclusion and exclusion criteria and provide written informed consent will be included in the protocol. The consent form details issues related to privacy, withdrawal from studies, and potential risks of studies among other items. The anorectal assessments are extremely safe. Subjects may experience the urge to defecate during rectal distention. Consistent with all our studies, distention will be terminated if patients experience severe discomfort. The listed side effects of alfuzosin include faintness/dizziness, vertigo, malaise, headache, hypotension (postural), nausea, abdominal pain, diarrhea, dry mouth, and asthenia. Hypotension is a listed side effect. However, even with chronic administration, the risk of hypotension is low. For example, in a study comparing alfuzosin 2.5 mg immediate release tid with 5 mg sustained-release twice daily in 2442 patients, the incidence of hypotension at 1 year was 1.6%; there were no clinically significant changes in systolic and diastolic blood pressure or heart rate between baseline and 24 months, i.e., -3.1mmHg, -1.4mmHg, and -0.05 bpm, respectively. In the largest experience of 13,389 patients (average age 67 years old) treated with alfuzosin 2.5 mg tid for benign prostatic hypertrophy for 3 months, two-thirds of the adverse events leading to discontinuation were vasodilatory and occurred in 2.7% of the patients: vertigo/dizziness (1.4%); malaise (0.6%); hypotension (0.4%), and headache (0.4%). While alfuzosin ER is approved by the FDA, the 2.5 mg immediate release formulation is not. Hence, this formulation will be imported from Europe after obtaining an IND from the FDA.
2. Data and Safety Monitoring Plan (DSMP)

- a) Subject Safety. Only subjects who are eligible based on pre-defined criteria, an interview and a physical examination, and screening laboratory tests will be enrolled. Study procedures are conducted by trained and experienced personnel. Interventions (alfuzosin and anorectal tests) pose a low risk to participants. Monitoring will be performed during and after the study by CRU RNs and the Study Coordinator. The PI will also review side effects. UPIRTSOs and non-UPIRTSOs will be reported per protocol to IRB and FDA (IND required for alfuzosin). Each study is reviewed and analyzed; study discussions and communications are generally by e-mail and stored. Study will be stopped if any rectal perforation occurs.
- b) Data Integrity. Only subjects who are eligible based on pre-defined criteria, an interview and a physical examination will be enrolled. Transcription of data is accurate and complete. Calculations will be standardized and accurate. The study technician will monitor data after every study. The PI will also review data after every 6 studies.
- c) Subject Privacy. Subjects will be consented in a private room. Adequate time for questions will be provided.
- d) Data Confidentiality. All records are maintained in password protected electronic files. Hard copies are filed in private offices.
- e) Product Accountability. Research Pharmacy will obtain and dispense medication. Unused medication will be collected from subjects at the end of the study and destroyed.
- f) Study Documentation. Documentation will be per established guidelines during the study (hard copy and electronic data capture). These files will be sampled annually.
- g) Study Coordination. Annual debriefing will be conducted to ensure expectations are clear and if educational needs exist.

### Appendix 1. Sample Stool Diary Card

Daily Diary												
Date: 												
If you had no bowel movements today, please check this box:  No bowel movements today.												
Please record the time you took the study medication today: _____ : _____												
Please record the time of today's breakfast: _____ : _____												
	Describe the consistency of bowel movement	Describe the Ease of Passage of bowel movement	Did you feel like you completely emptied your bowels?									
	1 hard lumps 2 lumpy sausage 3 cracked sausage 4 smooth sausage 5 soft lumps 6 Mushy 7 watery	1 Manual Disimpaction 2 Enema needed 3 Straining needed 4 Normal 5 Urgent wo/pain 6 Urgent w/pain 7 Incontinent	1 no 2 yes									
1   am  pm hr. min												
2   am  pm hr. min												
3   am  pm hr. min												
4   am  pm hr. min												
5   am  pm hr. min												
6   am  pm hr. min												
7   am  pm hr. min												
Have you had any unusual negative events today? No  Yes  (complete below) Event _____ Mild / Moderate / Severe Resolved / Ongoing												
Have you taken any medications other than those you routinely use today? No  Yes  (complete below) 
 
 Medication _____	Medication _____	Medication _____	
 
 Dose _____	Dose _____	Dose _____	
 
 Frequency _____	Frequency _____	Frequency _____	
 
				Medication _____	Medication _____	Medication _____	Dose _____	Dose _____	Dose _____	Frequency _____	Frequency _____	Frequency _____
Medication _____	Medication _____	Medication _____										
Dose _____	Dose _____	Dose _____										
Frequency _____	Frequency _____	Frequency _____										

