- iii. Able to communicate adequately with the investigator and to comply with the requirements for the entire study.

c) Exclusion Criteria for Controls; Items indicated with an asterisk (\*) are also exclusion criteria for patients

- i. Clinical evidence of significant cardiovascular, respiratory, renal, hepatic, gastrointestinal, hematological, neurological, psychiatric or other disease that may interfere with the objectives of the study and/or pose safety concerns.\*
- ii. Current symptomatic orthostatic hypotension or history of hypotensive response as defined by a reduction of  $\geq 30$  mmHg in systolic or  $\geq 20$  mmHg in diastolic BP.\*
- iii. Current symptoms of a functional gastrointestinal disorder assessed by questionnaire
- iv. Putative risk factors for pelvic floor trauma, i.e. six or more vaginal deliveries, birthweight >4500gms (macrosomia), or known 4th degree perineal tear
- v. Inability to withdraw medications prior to the baseline period and throughout the study (except as protocol defined rescue medications):
  - Medications that substantially alter GI transit \* including laxatives, magnesium and aluminum containing antacids, prokinetics, erythromycin, narcotics, anti-cholinergics, tricyclic antidepressants, SNRI and newer antidepressants
  - Selective serotonin reuptake inhibitor (SSRI) antidepressants are permissible at low, stable doses. All medications shall be reviewed and dis/approved by the principal investigator on a case by case basis. \*
  - Potent Cyp 3A4 inhibitors such as ketoconazole, itraconazole and ritonavir, nitrates and phosphodiesterase inhibitors \*

NOTE: stable doses of thyroid replacement, estrogen replacement, low dose aspirin for cardioprotection, and birth control (but with adequate backup contraception as drug-interactions with birth control have not been conducted) are permissible. \*
- vi. Stable dose of thyroxine will be permitted \*
- vii. Prolonged Q-Tc interval > 500 msec on ECG within the last three months\*
- viii. Estimated glomerular filtration rate (eGFR) < 60 mL/minute. \* Based on guidelines and recommendations from the National Kidney Disease Education Program (NKDEP) of the National Institutes of Health (NIH) and the Kidney Disease Outcomes Quality Initiative (KDOQI) of the National Kidney Foundation, the an eGFR using the Modification of Diet in Renal Disease (MDRD) Study

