**THE REST OF THIS PAGE IS INTENTIONALLY BLANK**

**Table 1. Schedule for Study Assessments and Monitoring**

[figure not shown]
	Screening	Acute Study	Bowel Symptoms (Alfuzosin – ER 10 mg)			
	Days –30 to 1	Day 1	Baseline Period (Days 3-16)		Treatment Period (Days 17-30)	
Procedure			Daily	Other	Daily	Other
Informed consent	X					
Review eligibility	X					
Physical examination	X					
Concomitant medication review	X	X				
Vital signs, weight	X	X 				
Serum creatinine, urine pregnancy test, ECG (12-lead)	X 					
Stool sample	X 			X 		
Anorectal study		X				
Randomization to treatment		X				
Study treatment administration		X				X 
Adverse event assessment		X		X 		X 
Stool diary (Appendix 1)			X		X	
Abdominal pain (Appendix 2)			X		X	
Global assessments (relief, severity) (Appendix 3)				Weekly		Weekly
Global assessment – satisfaction with treatment, (Appendix 4)	X			X (day 17)		X (day 31)
Other abdominal symptoms (Appendix 5)				Weekly		Weekly
Telephone contact				X  (q3-5 days)		X  (q3-5 days)

1. During the acute study, heart rate and blood pressure will be recorded at hourly intervals. Height (cm) and weight (kg) will be recorded at the screening visit but not on Day 1.
2. Urine pregnancy test to be performed for women of childbearing potential within 2 weeks of Day 1. Serum creatinine and ECG (12-lead) to have been done within three months of Day 1.
3. A single stool sample can be collected either before the acute study visit, or 3 days after the acute study visit, but before the treatment period.

4. Patients will be treated with placebo or alfuzosin ER (10 mg) once daily during this phase. While the protocol is planned for the treatment period to follow directly the baseline period, if needed for scheduling, there can be up to a 5-day interval between the baseline and treatment period.
5. Patients will be contacted by telephone every ~3-5 days between clinic visits to address questions, ascertain side effects and remind subjects to complete diaries. The final phone call will be within 5 days after completing the treatment period. Subjects will be asked to return unused medication by mail.

3. Experimental procedures. Items a-d below exclusively pertain to Part A,

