Alfuzosin (2.5 mg) has a mean bioavailability of 64%,  $t_{max}$  of 1.0 – 1.5 hours and a terminal  $t_{half}$  of 3-5 hours. The drug is extensively metabolized by the liver with only 11% of the administered dose excreted unchanged in the urine. This immediate release formulation, which is also manufactured by Sanofi-Aventis, not approved in the US but widely available in other countries, will be imported from UK (Xatral™, 2.5 mg) under an investigator-initiated IND (117098) from the FDA because the long  $t_{max}$  for alfuzosin ER limits its use in this acute study.

f) Stool collection. Using stool kits and standardized instructions, patients will collect stool samples according to the procedure in the Appendix. Stool samples will be frozen and stored in a -20°C freezer. The first stool specimen will be collected (a) without a laxative in controls and (b) if necessary, after their usual laxative regimen in patients. In Part B, the effects of alfuzosin extended-release (10 mg, Uroxatral) on bowel

symptoms will be evaluated. Since such use satisfies the requirements of 21 CFR 312.2 (b) (1), an IND is not required. We confirm that all the following apply to Part B of this study:

a) The investigation is not intended to be reported to FDA as a well-controlled study in support of a new indication for use nor intended to be used to support any other significant change in the labeling for the drug; and

b) The investigation is not intended to support a significant change in the advertising for the product; and

c) The investigation does not involve a route of administration or dosage level or use in a patient population or other factor that significantly increases the risks (or decreases the acceptability of the risks) associated with the use of the drug product; and

d) The investigation will be conducted in compliance with the requirements for institutional review set forth in 21 CFR 56 Institutional Review Boards and with the requirements for informed consent set forth in part 21 CFR 50 Protection of Human Subjects; and

e) The investigation will be conducted in compliance with the requirements of 21 CFR 312.7 - Promotion of Investigational Drugs.

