g) **Sequencing and analytical methods.** Using resources available in the UIUC-Mayo consortium, two complementary approaches will be utilized to analyze stool specimens from each subject. First, microbial DNA will be extracted from stool and tissue samples using standardized methods [33]. Phylotype profiles of the microbiome from control and constipated populations will be generated using deep rDNA hypervariable tag sequencing of the hypervariable V3-V5 region of the SSU rRNA gene, which has been validated for use with human microbiomes and is one of the methods of choice for the HMP. With the longer reads from the MiSeq (250x250 paired end reads), our sequencing will include both the V3-V5 RGTs making for a more optimal phylogenetic analysis [34]. Phylotype profiles of the mucosa-associated microbiome will be generated using rDNA sequencing of the hypervariable V3-V5 region, which has been validated for standard use by the human microbiome project. The 300 base pair reads will ensure a better optimal phylogenetic identification. Barcoding samples prior to sequencing will yield approximately 20,000 reads/sample, ensuring detection of both dominant (core microbiome) and poorly represented taxa (variable microbiome). Identifying the existent taxa, diversity, and ecological relationships within each sample requires that we process large volumes of 16S DNA sequence data. In order to accomplish this task we will follow protocols that we have quantitatively shown to be optimal. Paired end reads will be stitched, aligned, and classified using a custom pipeline (TORNADO v2.0).[35] Briefly, low base quality reads will be either trimmed or discarded,[36] and these reads will not be classified as a bacteria kingdom[37] or matched to the bacteria 16S rRNA secondary structure.[38] To evaluate the microbial diversity and abundance, UPARSE will be used for Operational Taxonomical Units (OTU) clustering,[39] and FastTree for phylogeny.[40] The 16S data will be clustered into OTUs at 97% sequence similarity, and the taxonomy will be assigned using the Ribosomal Database Project classifier. h) Effects of alfuzosin in bowel habits (Part B). During the first 2 weeks, bowel habits will be recorded at baseline. During the next 2 weeks, patients will be treated (double-blind) with placebo or alfuzosin (10 mg) ER once daily, which is FDA-approved dose for urinary symptoms. Symptom assessments are shown in Table 1 and in Appendices 1-5. Per eligibility criteria, subjects will discontinue medications which can affect GI transit during the baseline and treatment periods. Patients who need rescue medication, after three full days without a bowel movement, can receive 1-2 bisacodyl 5 mg tabs or a bisacodyl suppository (10 mg) or up to Fleet's enemas. In addition, patients who need relief of mild pain can use analgesic drugs such as NSAIDs and COX-2 inhibitors for up to two doses per week. During the procedure, intake of acetaminophen up to 1.5g per day in divided doses will be permissible.

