
#### 4. Data and statistical analysis

a) Part A. Anal manometry will be analyzed by established techniques and summarized as anal resting and squeeze pressures, rectal and anal pressure and rectoanal gradient during evacuation. Rectal pressure-volume relationships will be summarized by the  $P_{r_{half}}$  during rectal compliance, rectal capacity, pressure and volume sensory thresholds for first sensation, desire to defecate, and urgency. During

sinusoidal oscillation, average rectal pressures and the variability in pressures over 20 min will be summarized.

The analysis will be based on analysis of covariance (ANCOVA) models to assess the pre-dug period for intervention effects with subject status and intervention type as the primary factors (a check for order effects of the intervention sequences will also be made, and the corresponding pre-stress response will be included as a covariate). Models with a subject status by intervention type interaction will also be examined. During period 2, subjects will have been randomized to drug or placebo (balanced on subject status) and use the same intervention sequence as the pre-drug period). The analysis of the post drug period will also be based on ANCOVA models incorporating subject status, intervention type, treatment group, and corresponding interactions (a check for order effects will again be made). The corresponding responses from the pre-stress interval from period 1 and VAS scores for stress and arousal will be used as covariates,

b) Part B.

- i. Endpoints. Symptoms and Signs of Chronic Constipation. The effects of alfuzosin compared to placebo will be assessed by evaluating
  - Bowel habits using a daily diary (Appendix 1) to record stool consistency (Bristol Stool Form scale), frequency, ease-of-passage and sensation of complete bowel emptying (yes/no)
  - Daily Abdominal Pain Scores (Appendix 2) collected as (a) most severe daily score and (b) overall average daily score).
  - Global Patient Treatment Assessments reporting outcomes on a weekly basis (Appendix 3) including overall relief and severity of constipation
  - Global Patient reported outcomes on a 2-week basis (Appendix 5)
  - Patient reported outcomes of other abdominal symptoms (Appendix 6)

Two outcomes will be derived from primary data.

  - Weekly rate of SBMs: a bowel movement (BM) is considered an SBM if no laxative, enema or suppository was taken in the preceding 24 hours.

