  - Weekly rate of CSBMs: if the patient indicated that the SBM was associated with a sensation of complete bowel emptying, the SBM will be counted as a CSBM.
- ii. Analysis. Daily bowel diary responses will first be averaged over study periods (baseline and treatment) and in the case of stool frequency, per week. These responses will also be assessed using ANCOVA models, with the corresponding baseline value as the primary covariate. For stool frequency, the two weekly values will be assessed using a repeated measures ANCOVA model with the overall average baseline stool frequency value as a covariate. The global assessment scores (adequate relief and severity) will first be summed over the two treatment weeks, and then assessed using the Wilcoxon rank sum test. Individual adverse events (AEs) will be summarized by treatment group and the overall total frequency (per subject) of AEs assessed using the Wilcoxon rank sum test. The analyses will follow the intent to treat (ITT) paradigm with all

- patients randomized included in the analyses. Patients with missing values for a particular endpoint will have their missing values imputed using the corresponding overall mean value from all patients with non-missing data for that endpoint. An adjustment in the ANCOVA error degrees of freedom (subtracting one for each imputed value) will be made to account for the imputation. A similar adjustment for the Wilcoxon rank sum test (adjusting the degrees of freedom for the t-approximation) will also be examined.

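### The Part B diary asks only about medicines not routinely used, so a patient's own laxative may go unreported and the stool that follows may be counted as spontaneous

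*Combined protocol and SAP*

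**What the plan says.** **Outcome definition.** Section B.4.b (Part B, Endpoints) derives two weekly rates from the primary data. For the first, "a bowel movement (BM) is considered an SBM if no laxative, enema or suppository was taken in the preceding 24 hours". If the patient also reports complete emptying, "the SBM will be counted as a CSBM".

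**Laxative rules.** Exclusion criterion v (section B.1.c) lists laxatives under "Medications that substantially alter GI transit", and the asterisk there extends the criterion to patients. The Part B description (section B.3.h) repeats that "subjects will discontinue medications which can affect GI transit during the baseline and treatment periods". It also provides for rescue: "Patients who need rescue medication, after three full days without a bowel movement, can receive 1-2 bisacodyl 5 mg tabs", with a bisacodyl suppository or enemas as alternatives. The stool collection paragraph (section B.3.f) lets the first specimen be collected "if necessary, after their usual laxative regimen in patients".

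**Recording.** The Appendix 1 card has a field for the time of study drug and one question on other medication: "Have you taken any medications other than those you routinely use today". A Yes answer opens fields for medication, dose and frequency. In Table 1, the row "Concomitant medication review" is marked at screening and Day 1 only.

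**The concern.** The outcome rule needs every relevant intake, routine or not. The diary question leaves out medicines the patient routinely uses. For women with chronic constipation, a laxative may be one of those medicines.

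If such an intake goes unreported, the stool after it passes the SBM rule by default, and passes the CSBM rule too if emptying felt complete. This can happen in the baseline and the treatment periods. The same gap leaves Part B without an explicit check that laxatives stayed withdrawn. Intake that was never written down cannot be reliably recovered at analysis.

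**Working it through.** The documents give no figure for laxative use, so there is none to reproduce. The check traces each place where intake could be recorded in Part B, then asks what a gap would do to the treatment comparison.

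**1. Recording routes in Part B**

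| Route | Where | Captures a routine laxative tablet or suppository? |
|---|---|---|
| Diary medication question | Appendix 1 | Not if the patient reads it as exempting her own product |
| Ease-of-passage code 2 | Appendix 1 | No; it flags an enema for a given stool |
| Medication review | Table 1 | No; screening and Day 1 only, while the Part B baseline starts on Day 3 |
| Telephone contacts every 3-5 days | Table 1 footnote | Not listed; the stated purposes are queries, side effects and diary reminders |
| Product accountability | Section C.2.e | Rescue product not mentioned |

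**2. Who is affected**

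- A patient who lapses to her usual laxative and regards it as routine.
- A patient whose rescue product is also her routine product.
- Not a patient who usually takes something else and uses bisacodyl as rescue. On any reading, the question asks her to report it.

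**3. Timing**

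The card gives each stool a clock time but each medicine only a name, dose and frequency. Even a reported laxative cannot be placed exactly within the 24 hours before a stool.

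**4. Effect on the comparison**

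Let D be the true drug-minus-placebo difference in weekly SBMs. Let f_A and f_P be the mean weekly number of stools wrongly counted as SBMs on alfuzosin and placebo. Then:

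observed difference = D + f_A − f_P = D − (f_P − f_A)

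- If f_A = f_P, both rates rise and the difference is unchanged.
- If f_P > f_A, which is plausible if alfuzosin works and placebo patients need more rescue, the difference shrinks.
- If f_P < f_A, it grows.

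**5. Illustration on assumed values**

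Section B.5 says a difference of about 4 stools per week is detectable with 80% power at two-sided alpha 0.05. It gives no SD. Taking 18 patients per arm, the figure given for Part A, and a normal approximation:

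- multiplier = (1.960 + 0.842) × √(2/18) = 0.934
- implied SD = 4 / 0.934 = 4.28
- standard error = 4.28 × √(2/18) = 1.428
- power = Φ(observed difference / 1.428 − 1.960)

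Assume that D = 4 and that this SD applies to SBMs:

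| f_P − f_A (assumed, per week) | Observed difference | Power |
|---|---|---|
| 0 | 4.0 | 80% |
| 0.5 | 3.5 | 69% |
| 1.0 | 3.0 | 56% |
| 2.0 | 2.0 | 29% |

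The left column is not an estimate. The table shows sensitivity only.

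**The case against.** **The wording need not mislead.** The question is in the present tense, and patients have been told to stop laxatives before the baseline period. A withdrawn laxative is arguably no longer routine. A product taken only after three full days without a stool is also hard to call routine. Many patients may therefore report correctly. This stands: the error is possible, not certain. It does not remove the point, because an outcome rule should not depend on how each patient reads one word.

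**Rescue is mostly covered.** A reader might infer that rescue use in general goes unrecorded. The documents do not support that. Rescue escapes only when it coincides with the patient's own routine product, and some enemas are caught by the ease-of-passage code.

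**No large effect can be shown.** A reader might reason that fewer than three stools a week is the entry threshold, so that one false SBM a week inflates the rate by a third or more. Section B.1.b makes that frequency one of five symptoms, any two of which qualify, so women with three or more stools a week can enrol. Permission to use rescue also says nothing about how often it is used or left unreported. Nor do the documents say how many patients have a usual laxative; the stool collection paragraph gives no proportion. Any specific bias in SBMs per week would rest on unsourced rates.

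**Part B is secondary and parts of it are unseen.** Aim 5 is worded as exploration, and section B.7 says the sample size is primarily for the acute effects. Stool consistency, ease of passage, pain and global scores are not classified by laxative status. The card is labelled a sample, and Appendices 2 and 3 are not in the text available, so a further question there cannot be ruled out. All of this stands and lowers the severity.

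**Conclusion.** The point holds as a possible misclassification of the SBM and CSBM outcomes. The stated diary question can be answered so that a relevant laxative is left out, and the text available shows no other Part B record that captures tablets or suppositories.

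The documents do not support the stronger conclusion that habitual laxative users' induced stools will be counted as spontaneous, or that the Part B result is biased by a known amount. The size is unknown. The direction depends on whether unreported use differs between arms: equal use leaves the mean difference unchanged, and more on placebo shrinks a drug effect. The power figures above rest on an SD back-solved from the plan, on 18 per arm, and on assumed excesses. They carry no weight beyond illustration.

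This is a cheap improvement of minor severity.

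**What to change.** Add one daily item to the Appendix 1 card, for example: Did you take any laxative, suppository or enema today, including any you usually use? If yes, record which product and at what time. The clock time is needed because a same-day tick-box alone cannot apply a 24-hour rule.

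Keep the present question for other medicines. State in section B.4.b that SBM and CSBM are derived from the new item together with the stool times. Add a brief check of this item to the telephone contacts already scheduled every 3-5 days; it would also show whether laxatives stayed withdrawn.

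The cost is one more diary item per day for the patient, a short addition to calls already planned, and a revised card. No visit or procedure is added. The change concerns recording only and leaves the withdrawal and rescue rules as they are.
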